To explore the safety of Truvada when used as PrEP in combination with current recommendations for prevention of sexually transmitted infections and HIV in young women at substantial risk of HIV acquisition during pregnancy and lactation.

2.2 Primary Objective:

 To compare the frequency and seriousness of specific adverse events related to TDF/FTC in women and their children in Arm A (exposure to TDF/FTC) and Arm B (no exposure to TDF/FTC) during pregnancy until breastfeeding cessation.

2.3 Secondary Objectives:

- To estimate HIV incidence in women in ARM A with ARM B at delivery and at 18 months post-delivery.
- To determine the interdependency of adherence to a once daily oral TDF/FTC regimen and standard HIV prevention methods during pregnancy and postdelivery.
- To measure antiretroviral drug (TDF/FTC) level in women and their infants in association with adherence, safety and level of protection (plasma and breastmilk)
- To detect drug resistance among women who acquire HIV infection and correlate the treatment outcomes (after initiating immediate ARV treatment) with drug resistance
- To determine mother-to-child transmission of HIV among women who acquire incident infections during pregnancy and breastfeeding and the frequency of drug resistance in their infected babies

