6.0 STUDY TREATMENT CONSIDERATIONS

The drug to be used in this study is Truvada (tenofovir disoproxil fumarate/ emtricitabine) which is the antiretroviral drug to be used to prevent HIV acquisition. TRUVADA tablets are fixed dose combination tablets containing emtricitabine and tenofovir disoproxil fumarate. EMTRIVA is the brand name for emtricitabine, a synthetic nucleoside analog of cytidine. Tenofovir disoproxil fumarate (tenofovir DF) is converted in vivo to tenofovir, an acyclic nucleoside phosphonate (nucleotide) analog of adenosine 5'-monophosphate. Both emtricitabine and tenofovir exhibit inhibitory activity against HIV-1 reverse transcriptase.

6.1 Study product formulation and storage conditions

Study Drug : Emtricitabine-Tenofovir disoproxil fumarate FTC-TDF Truvada[®] Formulation: 200 mg/300 mg tablets

Appearance: Blue, capsule shaped, film-coated tablet that are debossed with "GILEAD" on one side

Storage: 25°C (77°F) - Excursions permitted between 15-30°C (59-86°F). Keep container tightly closed. Each bottle contains thirty tablets with a silica gel desiccant canister that should remain in the original container to protect the product from humidity.

6.2 Treatment Procedures

- ARM A: Pregnant women allocated to ARM A will initiate Truvada on the day of randomization and will continue throughout peripartum until cessation of breastfeeding and thereafter given an option to continue PrEP until 18 months postdelivery.
- ARM B: Pregnant women allocated to ARM B will only initiate Truvada at cessation of breastfeeding and thereafter given an option to initiate PrEP until 18 months postdelivery.

6.3 Treatment Schedule

The treatment schedule is a once daily uninterrupted course.

6.4 Study product procurement

The study site pharmacist will order Truvada from the manufacturer (Gilead Sciences).

6.5 Study product accountability

The study pharmacist will maintain complete accountability and storage condition records of all study products received from Gilead Sciences and subsequently dispensed to study participants. All study products will be stored at the site study pharmacy. All unused study products will be returned to Gilead Sciences after the study is completed and terminated.

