7.11 Follow-up Visits Post Delivery

Subsequent post-delivery visits will be scheduled for weeks 2, 6, 10, 14, 18 weeks, and thereafter monthly until 18 months postdelivery. Study product discontinuation could occur at cessation of breastfeeding for participants in the Treatment Arm who choose not to continue PrEP. And study product will be dispensed to participants in the Control Arm who choose to commence PrEP post cessation of breastfeeding. Study product will be distributed until 74 weeks and thereafter participants will be referred for ongoing PrEP at the nearest PrEP Demonstration Site at a public health clinic.

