7.12 At Follow-up Visits during Product Use

At follow-up visits antenatal week 4 through week 74, study staff will:

- Update contact information (when necessary);
- Conduct pill count of product returned by participant, and document any product returned to participant;
- Collect information on adherence to the daily pill-taking regimen;
- Conduct risk reduction counseling, including pre- and post-test HIV counseling and distribute condoms;
- Conduct study product adherence counseling;
- Conduct contraceptive counseling as appropriate, re-supply contraceptive method as needed;

- Collect blood by venepuncture (10ml) and:
 - Perform HIV rapid antibody testing according to the algorithm described at the enrollment visit.
 - ✓ Test for ALT, AST, creatinine and phosphorus. If results are abnormal, repeat regularly until resolution to ≤ Grade 1 or until stabilization. Any required followup will be done per local standard of care.
 - ✓ Store plasma and ULPC aliquots for HIV PCR testing, QA and confirmatory laboratory testing as needed. Also store one plasma aliquot (if sufficient sample available) and one serum aliquot for potential future HIV related research;
 - ✓ Screen and treat other STIs using the syndromic management approach
 - Collect cervical/vaginal swabs for storage and subsequent screening for STIs using molecular techniques.
- Conduct adverse event assessment as per the US Division of AIDS Adverse Event Reporting and Toxicity Grading;
- Conduct physical and/or pelvic examination if clinically indicated; and
- Record medications taken since last visit.
- Complete the Final Status CRF if the participant does not require further follow-up due to risk of Hepatitis B flare and/or HIV seroconversion.

Participants will be allowed to complete each follow-up visit up to five days prior to and two (for the week 4 follow-up visit) or four (for later follow-up visits) days after their next 4-week (28 days) target visit date. If participants complete a visit outside the given window for that specific visit, the visit will be regarded an interim visit and an appointment for the next scheduled visit will be given.

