7.13 Followup Visits for Infants

Infants will be assessed at birth, 26 weeks, 50 weeks and 74 weeks. In addition to a full physical examination, a blood sample will be drawn for assessing renal function (Creatinine Clearance) and Hormonal growth factors. For infants exposed to TDF/FTC an additional blood sample will be collected for a drug level assessment. At each visit the following growth parameters will be recorded: weight, height and head circumference. Infant feeding modality will be recorded at each visit. Cessation of breastfeeding is defined as 28 days after last exposure to breastmilk.

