7.21 Procedures for Assessing Safety

Participants will be asked one month after starting Truvada and at each subsequent scheduled visit whether they have had any admissions to hospital, or suffered from any significant illness that required medical attention. The site clinician will determine whether an illness meets the criteria for Serious Adverse Event (SAE) Reporting. SAEs will be reported to the UKZN BREC, Medicines Control Council and Department of Health. Participants will also be asked whether they have experienced any side effects.

Clinical assessments during pregnancy will be conducted as per the national guidelines for maternity care.

Maternal safety assessments during pregnancy and until 74 weeks study exit: All women will have bloods drawn for chemistry and haematological investigations at screening, enrolment, 2 weeks, 4 weekly until delivery, <72 hours of delivery, 2 weeks post delivery, 6 weeks, 10 weeks, 14 weeks and 4 weekly until 74 weeks (inclusive). Chemistry tests include liver function markers (ALT/AST/Phosporous), renal function (serum creatinine/urea/sodium/potassium), and bone density markers (serum calcium and magnesium).

Bone mineral content in the mother will be measured by DXA scan at 6 weeks postpartum, 6 months, 12 months and 18 months. Both Hip and Spine DXA scans will be done at above scheduled visits.

Within 72 hours of delivery, the participant with her maternity care record (MCR) will be reviewed by the study clinician. Fetal outcome in addition to other obstetric data will be extracted from the MCR. The following definitions will be used to document fetal outcome:

NON-VIABLE FETUS (MISCARRIAGE)

Less than 28 weeks* gestation and where there is no evidence of life at delivery. **STILL BIRTH** Gestational age of 28 weeks or more and where there is no evidence of life at delivery. **NEONATAL DEATH**** Death after a live birth whatever the duration of the pregnancy. **When the gestational age is not known, a legal weight cut-off of 1000 g is used.**

Maternal gestational age will be determined by clinical and obstetric assessments that will include an Ultrasound, measurement of symphysis fundal height and last menstrual date if known. Preterm delivery is defined as < 37 weeks. Moderate preterm delivery 32-35 weeks and severe preterm delivery <32 weeks.

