8.5 Definitions

Adverse Event:

An adverse event (AE) is defined as any untoward medical occurrence in a clinical research participant administered an investigational product and which may or may not have a causal relationship with the investigational product. As such, an AE can be an unfavorable or unintended sign (including an abnormal laboratory finding, for example), symptom or disease temporally associated with the use of an investigational product, whether or not considered related to the product. Study participants will be instructed to contact the study clinician to report any AEs their infants may experience.

Serious Adverse Event:

A serious adverse event (SAE) is any untoward medical occurrence that at any dose that results in death, is life threatening, requires inpatient hospitalization or prolongation of existing hospitalization, results in persistent or significant disability/incapacity, or is a

congenital anomaly/birth defect (April 1996 International Conference on Harmonisation (ICH), Good Clinical Practice: Consolidated Guidance, (ICH E6). Important medical events that may not be immediately life – threatening or result in death or hospitalization but may jeopardize the patient or may require intervention to prevent one of the outcomes listed in the definition above may also be considered to be serious. (October 1994 ICH guidance (E2A), Clinical Safety Data Management: Definitions and Standards for Expedited Reporting).

SUSAR: Suspected, Unexpected Serious Adverse Reaction:

Serious (see SAE definition above)

Related (i.e. there is a reasonable possibility that the AE may be related to the study agent)

Unexpected (see definition below)

Unexpected AE:

An AE, the nature or severity (intensity) of which is not consistent with the applicable agent information (Investigator's Brochure, package insert, or summary of agent characteristics).

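### Section 7.21 ties the scheduled admission and illness questions to starting Truvada, so read literally Arm B has none inside the primary comparison window

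*Combined protocol and SAP*

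**What the plan says.** Section 7.21 of the combined protocol and SAP sets when the solicited clinical questions begin: "Participants will be asked one month after starting Truvada and at each subsequent scheduled visit whether they have had any admissions to hospital". The same sentence goes on to significant illness. The site clinician's decision on whether an illness is a serious adverse event (SAE) and a question on side effects follow in the same paragraph. The side-effect question has no timing of its own.

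The Truvada start differs by arm. Under 6.2, Arm A starts on the day of randomisation, whereas "Pregnant women allocated to ARM B will only initiate Truvada at cessation of breastfeeding". Section 7.11 makes the Arm B start a matter of choice: "study product will be dispensed to participants in the Control Arm who choose to commence PrEP post cessation of breastfeeding". Section 7.8 likewise places the one-month interview for deferred women after breastfeeding has stopped. Section 7.13 dates that event: "Cessation of breastfeeding is defined as 28 days after last exposure to breastmilk".

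The primary objective (2.2) compares the frequency and seriousness of specific AEs between Arm A and an Arm B with "no exposure to TDF/FTC) during pregnancy until breastfeeding cessation". Section 8.5 defines an AE as "any untoward medical occurrence in a clinical research participant administered an investigational product", although the same paragraph also asks participants to report events in their infants. Section 10.4 summarises AE counts in pregnancy and after delivery for each arm, stratifies them by seriousness and compares the arms with Fisher's exact test.

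Section 7.12 points another way. It opens "At follow-up visits antenatal week 4 through week 74, study staff will" and its list includes "Conduct adverse event assessment as per the US Division of AIDS Adverse Event Reporting and Toxicity Grading". That sentence names no arm, but the section heading refers to visits during product use.

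**The concern.** A between-arm comparison of AE counts needs the same questions, asked on the same schedule, in both arms. In 7.21 the schedule depends on treatment: the clock starts with Truvada, which one arm takes from randomisation and the other cannot take until the primary window has ended. Section 8.5 reinforces this, because a woman who has not been given the product does not strictly fall under the AE definition.

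The trial is open label, so staff know which women are on Truvada when they decide whom to question. If they follow 7.21 and 8.5 as written, Arm A is asked at scheduled visits and untreated Arm B is not. Events that were never asked about cannot be recovered at analysis. An excess of clinical AEs or SAEs in Arm A could then partly reflect who was asked.

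**Working it through.** The plan gives no figure on this point, so there is none to reproduce. The check is a timing calculation followed by a side-by-side reading.

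**Inputs.** Arm A starts at randomisation and Arm B at breastfeeding cessation (6.2), the latter by choice (7.11). Cessation is 28 days, or 4 weeks, after last breastmilk exposure (7.13). The primary window closes at cessation (2.2). The first question comes one month after starting (7.21), taken here as 4 weeks. The last visit is week 74 after delivery (7.9).

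**Arm A.** First question = randomisation + 4 weeks. With enrolment at 14 weeks' gestation (Appendix 5) this is 14 + 4 = 18 weeks. With enrolment at 28 weeks, the average first visit in 3.1, it is 28 + 4 = 32 weeks. Both fall in pregnancy, inside the window.

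**Arm B.** Let L be the postnatal week of last breastmilk exposure.

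- Window closes: L + 4.
- Earliest Truvada start: L + 4.
- Earliest 7.21 question: (L + 4) + 4 = L + 8.
- Gap after the window closes: (L + 8) − (L + 4) = 4 weeks, whatever L is.

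Illustrative values of L, which are assumptions:

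| L | Window closes | Earliest question | Weeks left to week 74 |
|---|---|---|---|
| 26 | 30 | 34 | 40 |
| 52 | 56 | 60 | 14 |
| 66 | 70 | 74 | 0 |
| 67 | 71 | 75 | after the last visit |

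The 28-day definition does not drive the result. If cessation meant the last breastmilk exposure itself, the window would close at L and the first question would come at L + 4, the same 4-week gap. A woman who declines PrEP has no start date and so never reaches the first question.

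**The passages side by side.**

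- 7.21, with 7.8 and 8.5, ties questioning or the AE definition to product use. On the literal reading, Arm B has no scheduled question in the window.
- 2.2 and 10.4 assume AE data from both arms over the period compared.
- 7.12, by its visit range, would give both arms an AE assessment from antenatal week 4. By its heading it may not reach untreated Arm B women. If it does reach them, it contradicts 7.21; if it does not, the gap stays open. Either way the text needs reconciling.
- Elsewhere in 7.21 the safety bloods are set for all women, with no reference to Truvada. The section can therefore state a both-arm rule when one is meant.

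**The case against.** The strongest reply is that 7.12 already covers everyone. Its opening sentence has no arm restriction. Its list includes HIV testing and chemistry, which 7.20 and 7.21 require for all women, and Appendix 5 is a single schedule for both arms. A sensible site would probably apply it to both. This stands as a reason why bias is possible rather than certain. It does not settle the text, because the heading and the pill-count and adherence items in the same list concern product users.

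Second, Arm B is not left to chance reports. Appendix 5 marks a physical examination at every visit. Section 7.10 requires a maternity chart audit for complications since the last visit, and 7.21 has the clinician review the maternity record within 72 hours of delivery. These are scheduled and apply to both arms. They reduce the possible loss but do not replace a direct question about admissions and illness.

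Third, under-asking Arm B makes non-inferiority harder to show and would not manufacture reassurance. That is right about the direction, but a spurious excess of harm is still a wrong answer to the primary objective.

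A reader might infer more than the documents support:

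- **A conflict with section 8 as a whole.** Sections 8.0 to 8.4 deal with issues that may come to light and with events already known. They set no competing start point, and 8.5 shares the problem in 7.21.
- **Proof from the missing AE row in Appendix 5.** The table also omits pill counts and concomitant medication, which 7.12 orders, so the gap shows little.
- **No control group for infant creatinine and blood counts, because 7.21 mentions them for exposed infants.** That sentence does not exclude unexposed infants. Section 7.13 draws renal-function blood without arm restriction, and Appendix 6 schedules both tests without one.

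**Conclusion.** The inconsistency is real and should be fixed. Taken literally, 7.21 gives Arm B no scheduled admission or illness question inside the primary window. The earliest falls about 4 weeks after the window closes, and women who decline PrEP have none. This rests on the stated start rules and on taking one month as 4 weeks; it does not depend on how long a woman breastfeeds.

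Whether bias follows depends on practice. If 7.21 and 8.5 are followed as written, ascertainment of clinical AEs and SAEs is unequal and biased towards apparent harm in Arm A. If 7.12 is applied to both arms, there is no such bias. The documents give no basis for estimating its size.

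A reader might conclude that the whole primary safety comparison is compromised. It is not. Scheduled maternal bloods, physical examinations, DXA, the delivery chart audit and birth outcomes do not depend on the 7.21 questions. That includes preterm delivery, on which the sample size of 421 per group rests. What is exposed is the clinical AE and SAE count compared in 10.4.

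**What to change.** Three wording changes reconcile the passages.

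1. In 7.21, anchor the admission and illness questions to randomisation and ask them at the same scheduled visits in both arms. Replace the side-effect question with a neutrally worded symptom question, since untreated women cannot report side effects of a product they do not take.
2. In 8.5, define AEs for all randomised women and their infants, regardless of product.
3. In 7.12, state that the AE assessment applies to both arms and align the heading with the visit range.

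The case report forms should follow. Both arms already attend the same visits (7.9, Appendix 5), so none is added. The cost is slightly more AE data entry in Arm B.

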7.5 Enrolment

At screening, eligible participants will have been given a date to return to the clinic for enrollment. This date will be within two weeks of screening. If a participant does not return within 14 days of the screening visit, she will not be enrolled nor re-screened. At the enrollment visit, if the participant meets all eligibility criteria that can be known from the screening visit, study staff will obtain informed consent for study participation (Appendix 3). Informed consent will also be obtained for blood to be stored for future HIV related research (Appendix 4). A participant may refuse this procedure and still be part of the study. All study procedures listed in the Schedule of Evaluations for the mother (Appendix 5) and for the HIV unexposed infant (Appendix 6) will follow.

There will be a clinic interview, during which baseline demographic, clinical and behavioural data will be collected on a case record form. The behavioural and lifestyle information provided by the individual together with results from the screening for sexually transmitted infections will inform the development of a personalised plan for reducing their risk. A personalised invite to the sexual partner will be provided to all participants. The invitation is intended to encourage partners to test for HIV and be referred for ART if HIV positive. Partners will also be informed of their options for HIV prevention and what is available in the public sector.

Participants will receive supplies of condoms in quantities anticipated to last until the next visit. A participant can return between scheduled visits to obtain more condoms.

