The New Ballard method will be used to assess gestational age of neonate. In addition, neonates will be determined small for gestational age (SGA), average for gestational age (AGA) and large for gestational age (LGA).

Fetal Growth:

Fetal monitoring will include fetal growth and an ultrasound for fetal abnormalities. For fetal growth monitoring, we would measure the symphsis fundus height at each study visit, plot on graph against gestational age and compare with 10th, 50th and 90th centiles and previous measurements. Any measurement <10th centile or failure to increase will be referred for an ultrasound for further fetal assessment.

Infants exposed to TDF/FTC either in-utero or during breastfeeding will have chemistry (serum creatinine) and haematological (complete blood count) at birth, 26 weeks (6 month), 50 weeks (12 months), and 72 weeks (18 months).

Infant Bone Growth:

DXA scans of the lumbar spine and whole body of infants will be performed at 6 weeks, 6 months, 12 months and 18 months to determine BMC and bone growth.

Clinical Examination of Infants:

Clinical examination of infants at birth will be conducted as per standard of care prescribed in the SA paediatric guidelines. This will include examination for physical abnormalities.

Physical examination of infants will include OFC, weight, and length to monitor growth and also include assessments for neurodevelopmental milestones at 6 weeks, 3 months, 6 months, 12 months and 18 months.

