APPENDIX 5 SCHEDULE OF EVENTS FOR MOTHER

		ANTENATAL			LABOUR AND DELIVERY	POSTNATAL					
	SCREENING 1 ^{sr} ANTENATAL VISIT	2 [№] ANTENATAL ENROLMENT 14W	3 RD ANTENATAL 2 WEEKS	SUBSEQUENT 4 WEEKLY ANTENATAL	<72 HOURS POST DELIVERY	2 WEEKS	6 WEEKS	10 WEEKS	14 WEEKS	SUBSEQUENT 4 WEEKLY POSTNATAL	74 WEEKS/STUDY EXIT
Study Informed Consent	Х	Х									
Storage Informed Consent		х									
Documented HIV test result	Х	~									
HIV Risk Assessment	Х										
Medical History	Х										
Hx, Signs/Sx of STIs	Х		Х	Х	Х	Х	Х	Х	Х	Х	Х
Pregnancy Ultrasound	Х										
Obstetric Assessments	Х	Х	Х	Х							
DXA Scan Hip and Lumbar Spine							Х			X*	Х
Physical Exam	Х	Х	Х	Х	Х	Х	Х	Х	Х	Х	Х
Randomisation		Х									
Sexual Behaviour Questionnaire	Х	Х	Х	Х	Х	Х	Х	Х	Х	Х	Х
Drug Adherence Interview			Х	Х	Х	Х	Х	Х	Х	Х	Х
Condom Usage Interview		Х	Х	Х	Х	Х	Х	Х	Х	Х	Х
Risk Reduction Counselling		Х	Х	Х	Х	Х	Х	Х	Х	Х	Х
Laboratory Investigations											
RPR Test	2ml								2mL		2mL
HIV Rapid Test (finger prick)	Х	Х	Х	Х	Х	Х	Х	Х	Х	Х	Х
Hep B Surface Antigen	2ml						2mL				2ml
ALT/AST/Phosporous		2ml		2mlª				2ml		2mlª	
CBC	2ml		2ml	2mlª	2mL				2mL	2mlª	
Serum Creatinine	2mL		2mL	2mL		2mL		2mL	2mL	2mL	2mL
Stored EDTA Plasma, DBS /cell pellets		10mL	10mL	10mL	10mL	10mL	10mL	10mL	10mL	10mL	10mL
Stored Breast Milk (during BF only)						10mL	10mL	10mL	10mL	10mL	10mL
Cervical Vaginal Swabs		Х	Х	Х			Х	Х	Х	Х	Х
TOTAL BLOOD VOLUME	8ml	12ml	14ml	16ml	12ml	12ml	12ml	14ml	14ml	16ml	12ml

* DXA scan at 6 and 12 months

APPENDIX 6

SCHEDULE OF EVENTS FOR HIV UNEXPOSED INFANTS

	BIRTH	6 WEEKS	26 WEEKS	50 WEEKS	72 WEEK/STUDY EXIT VISIT
Physical Exam	Х	Х	Х	Х	Х
Growth Parameters and neurodevelopmental milestones	Х	X	Х	Х	X
DXA Scan Lumbar Spine and Whole Body		Х	Х	Х	X
Laboratory Investigations					
CBC	2mL	2ml	2mL	2mL	2mL
Serum Creatinine	2mL	2ml	2mL	2mL	2mL
Stored DBS	Х	Х	Х	Х	Х
TOTAL BLOOD VOLUME	4ml	4ml	4ml	4ml	4ml

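### The protocol contradicts itself on which infants have safety creatinine and blood counts, and when: section 7.21 ties the tests to TDF/FTC exposure, section 7.13 and Appendix 6 do not.

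*Combined protocol and SAP*

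**What the plan says.** Three places set out infant blood tests.

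- Section 7.21 (safety assessments): "Infants exposed to TDF/FTC either in-utero or during breastfeeding will have chemistry (serum creatinine) and haematological (complete blood count) at birth", and then at 26, 50 and 72 weeks. It does not mention unexposed infants.
- Section 7.13 (infant visits) covers infants generally, at birth, 26, 50 and 74 weeks: "a blood sample will be drawn for assessing renal function (Creatinine Clearance) and Hormonal growth factors". It adds one item by exposure: "For infants exposed to TDF/FTC an additional blood sample will be collected for a drug level assessment".
- Appendix 6 is titled "SCHEDULE OF EVENTS FOR HIV UNEXPOSED INFANTS". It lists CBC and serum creatinine, 2 mL each, at birth and at 6, 26, 50 and 72 weeks, with no split by arm or drug exposure. Its bottom row reads "TOTAL BLOOD VOLUME 4ml 4ml 4ml 4ml 4ml". Section 7.5 puts it into effect after enrolment: the procedures "for the HIV unexposed infant (Appendix 6) will follow".

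The primary objective (section 2.2) is "To compare the frequency and seriousness of specific adverse events related to TDF/FTC in women and their children in Arm A" and in Arm B. Section 8.5 allows an abnormal laboratory result to be an adverse event, and section 10.4 compares the number of adverse events between arms with Fisher's exact test.

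**The concern.** Arm B mothers start Truvada only after breastfeeding has stopped (section 6.2), so their infants have no exposure to study PrEP in the womb or through milk. A rule that tests exposed infants is therefore close to a rule that tests Arm A.

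If staff worked from 7.21, ordinary background abnormalities in creatinine or blood counts would be found and recorded in Arm A and mostly go unseen in Arm B. The laboratory part of the child-safety comparison would lose its randomised control. A pooled infant adverse-event count would tilt against PrEP even if the drug did nothing. Samples not taken at birth or six months cannot be recovered later.

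**Working it through.** **Step 1. The three rules side by side.**

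| | 7.13 | 7.21 | Appendix 6 |
|---|---|---|---|
| Infants covered | infants generally | those exposed to TDF/FTC | HIV-unexposed, either arm |
| Creatinine / renal function | yes | yes | yes |
| CBC | not mentioned | yes | yes |
| Ages (weeks) | birth, 26, 50, 74 | birth, 26, 50, 72 | birth, 6, 26, 50, 72 |
| Exposed infants only | extra drug-level sample | the whole panel | nothing |

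For unexposed Arm B infants, creatinine is supported by 7.13 and Appendix 6, and CBC by Appendix 6 alone. The 6-week draw is in Appendix 6 only. The last draw is at 72 weeks in two places and 74 in the third. No passage ranks the three.

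**Step 2. Is the exposure wording in 7.21 a restriction?** The word only is absent. But the same section gives maternal bloods to all women, and describes infant DXA with no exposure condition. The condition is attached to infant bloods alone, and it does no work unless it limits who is tested. Restriction is the natural reading, though it remains an inference.

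**Step 3. How many Arm B infants would 7.21 still test?** Women who seroconvert move to treatment containing TDF/FTC (section 6.11), so an infant still in utero or breastfed becomes exposed. Inputs from section 10.3: control-arm HIV incidence of 3 per 100 person-years over 0.5 years and 6 per 100 over 1.5 years; 44 infections expected among 346 control women (stated as 12.72%); 442 women per arm.

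- From the rates: 1 - exp(-(0.03 × 0.5 + 0.06 × 1.5)) = 1 - exp(-0.105) = 10.0%. Then 0.0997 × 442 = 44 women.
- From the stated count: 44/346 = 12.7%, which reproduces the plan's figure. Then 0.1272 × 442 = 56 women.

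These are upper limits for this route, because women infected after weaning do not expose the infant and the others do so only from the time treatment starts. Section 6.11 also lets Truvada for newly acquired hepatitis B override allocation; the documents give no rate for that.

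**Step 4. Size of the imbalance if 7.21 were followed.** Assume every Arm A infant is tested, 10.0-12.7% of Arm B infants are tested, the true abnormality rate is the same in all infants, and untested infants are counted as event-free. The expected ratio of laboratory events, Arm A to Arm B, is then 1/0.127 to 1/0.100, or about 8 to 10, whatever the background rate.

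As an illustration only, take 421 per arm and 12.7% of Arm B tested (421 × 0.127 = about 54 infants). The documents give no background rate, so 2% to 10% is assumed:

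| Assumed rate | Arm A events | Arm B events | Two-sided Fisher p |
|---|---|---|---|
| 2% | 8 | 1 | 0.038 |
| 3% | 13 | 2 | 0.007 |
| 10% | 42 | 5 | 1e-8 |

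These p-values describe a naive pooled count under the 7.21 rule. They do not predict the trial's result.

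**The case against.** The strongest reply is that the protocol, taken as a whole, does schedule these tests in both arms. Appendix 6 is the operational schedule, section 7.5 applies it without regard to arm, and section 7.13 separates a general renal sample from an exposure-only drug-level sample. On that view 7.21 is the outlier, and one-arm sampling was never a design choice. This stands, and it is why the point is an inconsistency.

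A reader of 7.21 alone might infer that the control arm has no infant laboratory data. The documents do not support that: 7.13 and Appendix 6 schedule it. Even under 7.21 some Arm B infants would be tested, and clinically indicated tests could add a few results.

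It is also fair to say that the main infant outcomes in section 10.2 are bone mineral density and growth. Infant creatinine and CBC are not named there, the DXA scans and growth measurements are not tied to exposure, and the sample size rests on preterm delivery. The illustration uses an assumed rate and counts untested infants as event-free; an analysis confined to tested infants would show missing control data instead of a false signal.

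None of this removes the conflict. Staff who open the safety section find a narrower rule than staff who open the appendix, and nothing tells them which to follow. Confining the analysis to tested infants would not rescue the comparison either: the Arm B infants tested under 7.21 would be a selected group, mostly with mothers who have acquired HIV and take combination treatment.

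**Conclusion.** The concern holds as an internal contradiction of moderate severity. Sections 7.13 and 7.21 and Appendix 6 disagree on which infants have creatinine and CBC, and at what ages. The harm is conditional: it arises only if 7.21 is followed as naturally read. In that case scheduled laboratory testing would reach all of Arm A but, through maternal seroconversion, at most about 10-13% of Arm B (44 to 56 of 442). With no drug effect, a pooled count would then show roughly 8 to 10 times as many laboratory events in Arm A. Those figures rest on the protocol's own incidence assumptions, equal background rates and no allowance for hepatitis B treatment or clinically indicated tests. The bone and growth comparisons stand either way.

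**What to change.** - In 7.21, replace the exposure condition on infant bloods with a statement that infants in both arms have serum creatinine and CBC. Naming the arms also covers infants of women who seroconvert, whom the title of Appendix 6 leaves out.
- Use one list of ages in 7.13, 7.21 and Appendix 6. Settle whether the 6-week draw applies and whether the last is at 72 or 74 weeks, and add CBC to 7.13, so both arms are sampled at the same ages.
- Keep only the drug-level sample restricted to exposed infants, as 7.13 already has it.
- If any infants have already been followed under 7.21, report the number tested by arm and visit, and do not count untested infants as event-free.

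The cost is a short wording amendment. If the site had planned on 7.21, control infants would have additional draws, but these are the ones Appendix 6 already lists (2 mL + 2 mL = 4 mL per visit).
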